Main Analyses: First, we will fit a series of negative binomial regression implemented in the SAS® GENMOD procedure with each fracture outcome as the dependent variable; duration of follow-up as an offset to account for each participant's exposure; treatment arm as the main independent factor of interest; and any covariates deemed important as additional independent variables in sensitivity analyses. The incident rate ratio and its statistical significance at $\alpha=0.05$ level for the primary outcome of all new fractures will serve as a formal test of the main fracture reduction hypothesis (H1). Second, we will fit a series of linear mixed models using the SAS® MIXED procedure with raw and percent change each from baseline in each of the continuous outcomes representing laboratory measures related to safety as the dependent variable; treatment arm, follow-up time point (12-/24-/36-month, as available) and their interaction as the

fixed effects of interest; and a subject random effect. For some measures, we will fit simpler models (due to only one planned post-infusion assessment) using the GLM procedure with raw and percent change each as the dependent variable, and treatment arm as the main factor of interest. We will appropriately construct sets of contrasts to test various hypotheses of interest by comparing the said change over time between the two arms. Third, we will fit a series of logistic regression models using the SAS® LOGISTIC procedure with each incident dichotomous adverse event during the 36-month follow-up (any and specific types of adverse events) as the dependent variable, and treatment arm as the independent factor of interest. The resulting odds ratios and levels of significances will be used to test the specific hypotheses for Aim 2. We will repeat all main analysis after stratification by institutional setting (assisted living/nursing home).

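### The mixed models for the laboratory safety measures name a subject random effect but no residual covariance, so contrasts at or between visits have wrong standard errors if the spread of change differs by visit.

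*Protocol*

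**What the plan says.** The only specification is in the Protocol, Statistical Considerations, under Main Analyses. The SAP holds just the overview paragraph and does not mention the laboratory models.

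- **Procedure and response:** "we will fit a series of linear mixed models using the SAS® MIXED procedure with raw and percent change each from baseline", applied to "each of the continuous outcomes representing laboratory measures related to safety as the dependent variable".
- **Fixed effects:** "treatment arm, follow-up time point (12-/24-/36-month, as available) and their interaction as the" terms of interest.
- **Within-subject dependence:** the sentence ends "fixed effects of interest; and a subject random effect". Neither document names a residual covariance structure, variances that differ by visit, empirical standard errors, or a rule for choosing among structures.
- **Use of the model:** "We will appropriately construct sets of contrasts to test various hypotheses of interest by comparing the said change over time between the two arms".
- **Exception:** some measures go to a simpler GLM, "due to only one planned post-infusion assessment".

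The Protocol's Study Objectives list the laboratory safety outcomes (H&H, calcium, albumin, alkaline phosphatase, 25-OH vitamin D, eGFR). The documents do not say which of these have more than one follow-up assessment and so fall under the mixed model.

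**The concern.** A subject random intercept with independent, equal-variance residuals is compound symmetry. Change at month 12 then has the same variance as change at month 36, and months 12 and 36 are as strongly correlated as months 12 and 24. For change from baseline this holds if each woman has a stable level plus independent error. It fails if women drift at different rates over three years, because the variance of change then grows with time.

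The consequence falls on the arm-by-time contrasts. A contrast at one visit takes its standard error from a variance pooled over all three. Where the true variance exceeds the pooled one, intervals are too short and false signals too frequent. Where it is smaller, intervals are too long and a real safety difference is easier to miss. When later visits are missing, the likelihood estimates also lean on the covariance model. The same model is reused in the repeats by institutional setting and in the interaction and subgroup fits for Aim 3(a).

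**Working it through.** The plan states no figure here (no SD, correlation, sample size or attrition rate for these measures), so there is nothing to reproduce. The check asks how far the standard errors could be off.

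**Inputs**
- From the Protocol: three visits, arm-by-time model, subject random effect.
- Assumed: SDs of change, correlations, dropout, and a two-sided 5% level. The Protocol attaches its level only to the fracture test ("its statistical significance at $\alpha=0.05$ level for the primary outcome of all new fractures").

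**1. What the model implies.** With random-intercept variance s_b² and residual variance s_e², the variance at every visit is s_b² + s_e², and the correlation for every pair is s_b²/(s_b² + s_e²).

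**2. Contrast at one visit, complete data.** The fitted variance is the mean of the three visit variances, so

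- model SE / true SE at visit t = √(mean SD²) / SD_t
- actual error = 2 × [1 − Φ(1.96 × ratio)]

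SDs 8/9/10: mean variance (64 + 81 + 100)/3 = 81.67, pooled SD 9.037.

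SDs 8/10/12: mean variance (64 + 100 + 144)/3 = 102.67, pooled SD 10.132.

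| Assumed SDs | Visit | SE ratio | 1.96 × ratio | Actual error |
|---|---|---|---|---|
| 8/9/10 | 12 | 9.037/8 = 1.130 | 2.214 | 2.7% |
| | 24 | 9.037/9 = 1.004 | 1.968 | 4.9% |
| | 36 | 9.037/10 = 0.904 | 1.771 | 7.7% |
| 8/10/12 | 12 | 10.132/8 = 1.267 | 2.482 | 1.3% |
| | 24 | 10.132/10 = 1.013 | 1.986 | 4.7% |
| | 36 | 10.132/12 = 0.844 | 1.655 | 9.8% |

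With constant SD the ratio is 1 at each visit and the error is 5%. With SDs falling in the ratio 1.5/1.25/1 the pattern reverses: 9.8% at month 12 and 1.3% at month 36.

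**3. Contrast between visits, month 36 against month 12.** Assume correlations of 0.6 for adjacent visits and 0.5 for months 12 and 36. The model variance of the within-subject difference is 2 × (mean variance − mean covariance).

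- 8/9/10: mean covariance (43.2 + 54 + 40)/3 = 45.73. Model 2 × (81.67 − 45.73) = 71.87; true 64 + 100 − 80 = 84. Ratio √(71.87/84) = 0.925, error 7.0%.
- 8/10/12: mean covariance (48 + 72 + 48)/3 = 56. Model 2 × (102.67 − 56) = 93.33; true 64 + 144 − 96 = 112. Ratio 0.913, error 7.4%.

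**4. Contrast averaged over visits.** Its variance depends only on the sum of all nine covariance entries. With complete data the fitted model reproduces that sum: for 8/9/10, (3 × 81.67 + 6 × 45.73)/9 = 57.71 under both the model and the truth. This contrast is not distorted.

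**5. Dropout.** REML simulation of the planned model: 150 per arm, 2,000 runs, correlations 0.7 and 0.5, random loss at each of months 24 and 36. Month-36 error:

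| Relative SDs | No loss | 15% per visit | 25% per visit |
|---|---|---|---|
| 1/1.1/1.2 | 6.6% | 8.3% | 8.5% |
| 1/1.25/1.5 (same ratios as 8/10/12) | 10.6% | 12.6% | 12.6% |
| 1/1.5/2 | 12.9% | 15.9% | 16.6% |

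With constant SD and a common correlation of 0.6, the error at each visit stayed between 4.8% and 5.8%.

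**6. Effect of the fix.** An unstructured covariance estimates each visit's variance separately, so the ratio targets 1. In simulation with 100 per arm, correlations 0.6/0.5 and 0% or 20% loss per visit (2,000 runs), it gave 4.4% to 5.9% at every visit. A smaller check (600 runs, normal reference) gave 4.8% to 7.0%; the Monte Carlo standard error there is √(0.05 × 0.95/600) = 0.9 points.

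**The case against.** The strongest objection is that the premise is missing from the documents. Nothing in them shows that the SD of change grows, or differs at all, by visit. If SD and correlation are constant, the planned model is right. This stands: the distortion is conditional, and its size is a range under assumption.

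A reader might go further and infer any of the following, which the documents do not support:

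- **That the plan forces equal variances.** The text names a random effect and is silent on the residual structure. PROC MIXED would allow a REPEATED structure as well. But nothing commits to one, and the model as written is compound symmetry.
- **That month-36 intervals will be too narrow.** This needs SDs that rise. With falling SDs it is month 12 that suffers.
- **That tests at single visits are planned.** The contrasts are described only as comparing change over time between arms. Single-visit and between-visit contrasts are natural readings of an arm-by-time model, but they are not spelled out. An average over visits would be unaffected with complete data.
- **That attrition will be heavy.** The Protocol foresees partial follow-up because of death, dropout or moving, and gives no rate.
- **That particular measures, such as eGFR, are affected.** The documents do not say which measures have repeated follow-up.

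There is also some mitigation. Descriptive statistics of change by arm and time point come first and would show unequal spread, and exploratory robustness analyses are promised. Neither sets a covariance rule, so a structure could still be chosen after the data are seen.

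**Conclusion.** The point holds in conditional form and is minor. For laboratory safety measures with more than one follow-up assessment, the named model carries an equal-variance, equal-correlation assumption that the documents neither justify nor relax.

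Under assumed SDs of 8/9/10 to 8/10/12 with complete data, the actual error of a two-sided 5% contrast is 7.7% to 9.8% at month 36 and 2.7% to 1.3% at month 12, with month 24 near nominal. Dropout tends to raise the month-36 figure.

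The point does not touch the primary negative binomial fracture analysis, the logistic adverse-event models, the measures sent to GLM, or the arm contrast averaged over visits with complete data.

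**What to change.** State in the SAP that, for measures with more than one follow-up assessment, the within-subject covariance is unstructured by visit. In PROC MIXED, replace the random subject effect with `REPEATED visit / SUBJECT=id TYPE=UN` and use Kenward-Roger degrees of freedom (`DDFM=KR` on the MODEL statement). Name the fallback in advance: heterogeneous Toeplitz, or heterogeneous compound symmetry, if the unstructured fit does not converge. Both keep a separate variance for each visit. State also which contrasts will be reported (single-visit, between-visit or averaged).

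The cost is a line of code and a few sentences, with no new data. The downside is small: six covariance parameters (three variances and three covariances) instead of two. In small strata of the institutional-setting and subgroup repeats, the fallback may be needed. If the analysis has already been run, the same model can be reported as a sensitivity analysis.

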Indices of Bone Mineral Metabolism: Serum will be assayed for 25-hydroxyvitamin D2/D3 for the secondary aim. We will collect serum for bone turnover markers at baseline and M36 for responder analysis for the exploratory aim (60, 65-67, 132, 133). To assess bone resorption, we will measure serum CTX. We will assess bone formation with P1NP. Serum will be archived for future analyses.

Trabecular Bone Score (TBS): TBS, a new gray-level texture measurement is evaluated in the same region of interest as the spine BMD using the iNsight Software version 1.9 (54-58). TBS utilizes the 2-D DXA spine images and provides 3-D microarchitectural images and parameters (57, 59). The precision for TBS ranged from 1.1 to 1.9% (55). In previous studies, TBS was independent of BMD for fracture prediction and significantly improved risk protection (80, 81). TBS is only minimally affected by sclerosis/osteoarthritis (57). For the exploratory aim, we will examine TBS from DXA images.

Eligibility Criteria

Inclusion Criteria:

Our goal is to include older women with osteoporosis or low bone mass (with fracture risk) unless there is a known contraindication to therapy. We will enroll ambulatory women age ≥ 65 years including those using assistive devices to maximize generalizability, if they:

- 1) Reside in long-term care (LTC) including Managed Senior Communities which provide the following: (a) An environment engineered to prevent falls (handrails, ramps) and are ADA accessible; (b) Facilitate access to medical attention (pull cords, life-alerts, or other electronic means); (c) ADA accessible transportation services available; (d) Provide or coordinate meals; (e) Secure building (automatically locked door or buzzer system, security cameras).
- 2) Have a) osteoporosis by axial bone density (spine, hip or forearm BMD T-score ≤ -2.5 SD)(99,100); or b) a previous adult fragility fracture of the spine or hip; or, c) would be treated based on FRAX (101,102) NOF treatment thresholds of a 10 year risk of $\geq 20\%$ for a major osteoporotic fracture or $\geq 3\%$ for hip fracture using femoral neck BMD (103).

Follow-up Extension Inclusion Criteria:

- 1) Complete Month 36 Visit on or before July 31, 2021.

Exclusion Criteria:

We will exclude:

- 1) Men because osteoporosis is less common in men and our initial ZEST 1 study only included women.
- 2) Institutionalized women with subacute illnesses surviving or discharged in < 3 years.

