Findings from the proposed trial will be most useful if (a) we can also identify a target sub-population of the long-term care that is most likely to benefit from zoledronic acid and/or least likely to experience side effects; and (b) we can speculate whether fracture reduction or non-reduction in women, despite improvement in BMD, depends on bone microstructure as measured by TBS. Therefore, using several techniques, some with an exploratory data mining philosophy, we will identify such sub-populations to address Aim 3(a). First, we will include all baseline clinical and laboratory characteristics, one-at-a-time, as an additional fixed effect in the models above, along with an interaction term with treatment group. Statistical significance of the interaction term will be interpreted as a patient baseline characteristic whose levels exhibit potentially differential treatment effects and/or safety profiles. Second, we will stratify analyses by such baseline criteria to actually obtain preliminary estimates of subgroup-specific treatment effects/safety differences. Third (data mining), using only the active arm, we will fit a series of logistic regression models using the SAS® LOGISTIC procedure and classification tree models using Salford Predictive Miner® software (Salford Systems, Inc., San Diego, California) with incident fracture as the dichotomous response variable; and baseline characteristics as predictors. Logistic models are more efficient when associations are linear, and hard-to-discover higher order interactions and non-linearity and/or multicollinearities among predictors do not exist, while classification tree models are more efficient when they do exist. Thus we will use both methods to obtain areas under the receiver operator characteristic curve (AUROCC) to quantify predictive accuracy, and use the results from the method with a greater AUROCC. For logistic regression we will use the backward elimination and for classification trees minimum misclassification-complexity cost tree to guard against overfitting. We will use the method of DeLong to obtain statistical significance of the differences in predictive accuracy between the models. For predicting improvements in continuous BMD change outcomes, we will employ a similar approach but with standard multiple linear regression and regression tree models and proportion of explained variance (R²) to quantify predictive accuracy.

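### In exploratory Aim 3(a), the between-arm search for women who benefit most tests the fracture rate ratio, and no absolute fracture benefit is planned beside it.

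*Protocol*

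**What the plan says.** The relevant text is in the protocol, Statistical Considerations. The SAP repeats only the overview paragraph and says nothing on Aim 3.

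- **Goal.** The investigators want to "identify a target sub-population of the long-term care that is most likely to benefit from zoledronic acid and/or least likely to experience side effects".
- **Technique 1.** Every baseline clinical and laboratory characteristic enters, one at a time, "as an additional fixed effect in the models above, along with an interaction term with treatment group". The decision rule is: "Statistical significance of the interaction term will be interpreted as a patient baseline characteristic whose levels exhibit potentially differential treatment effects and/or safety profiles".
- **Technique 2.** Next, "we will stratify analyses by such baseline criteria to actually obtain preliminary estimates of subgroup-specific treatment effects/safety differences". No effect scale is named.
- **Technique 3.** "Third (data mining), using only the active arm, we will fit a series of logistic regression models", together with classification trees, to predict incident fracture. There is no control arm and no interaction term.
- **The models referred to.** Under Main Analyses, fractures are modelled by negative binomial regression with a follow-up offset, and the effect measure is a ratio: "The incident rate ratio and its statistical significance at" the 0.05 level forms the primary test. Adverse events use logistic regression and odds ratios. Laboratory safety measures use linear models of raw and percent change. All main analyses are repeated by institutional setting.

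Neither document plans a fracture rate difference, a 3-year risk difference, or benefit by predicted baseline risk.

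**The concern.** Who benefits most is, at least in part, a question about how many fractures are prevented. That depends on the relative effect and on the rate without treatment. An interaction in a log-link model sees only the first. A drug that cuts every woman's rate by the same proportion prevents more fractures in women at higher risk, yet the interaction is then exactly zero.

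The plan could therefore report that no target group exists, or name one that arose by chance, while a real gradient in absolute benefit goes unreported. It could also favour low-risk women with a better ratio but few fractures prevented. This is separate from multiplicity: perfectly calibrated interaction tests would miss the gradient too.

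**Working it through.** The documents give no absolute-benefit figure, sample size or dispersion, so there is no planned figure to reproduce.

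**1. What the interaction measures.** For arm A and characteristic X, the technique 1 model is

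log(rate) = b0 + b1·A + b2·X + b3·A·X.

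exp(b3) is a ratio of rate ratios. If the rate ratio RR is the same at every level of X, then b3 = 0. The rate difference at a control rate λ is λ(1 − RR). Between two levels of X it varies by λ_high/λ_low, whatever the value of RR.

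**2. Size at the protocol's own gradient.** Inputs:

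- Women with hip or vertebral fractures have 2-3x the risk of a future fracture (Scientific Background), read here as a rate ratio k of 2 or 3.
- Nonvertebral fracture incidence is 11% per year (same section), read as 0.11 per woman-year.
- RR = 0.65, from the 35% reduction in all clinical fractures in the pivotal trial (Study Design & Methods). This is illustrative.
- Half the women have a prior fracture (assumption).

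The rate without prior fracture is 0.11/(0.5 + 0.5k). The rate difference is 0.35λ. The 3-year risk difference is exp(−0.65·3λ) − exp(−3λ), with a constant hazard.

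| k | λ without / with prior fracture | Rate difference per 100 woman-years | 3-year risk difference | Ratio of risk differences |
|---|---|---|---|---|
| 2 | 0.0733 / 0.1467 | 2.57 / 5.13 | 6.4% / 10.7% | 1.67 |
| 3 | 0.0550 / 0.1650 | 1.93 / 5.78 | 5.0% / 11.5% | 2.29 |

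The rate differences vary 2- and 3-fold. If the lower rate is instead varied from 0.0223 to 0.11, the ratio of 3-year risk differences is 1.53 to 1.89 for k = 2 and 1.75 to 2.69 for k = 3. The 0.0223 is −ln(0.8)/10, from the FRAX entry threshold of 20% in 10 years.

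**3. What the tests would show.** A simulation used 600 trials per sample size, control rates of 0.11 and 0.0223, RR 0.65 in both groups, a characteristic present in half the women, dispersion 0.5, and two-sided 0.05. The sample sizes and dispersion are assumptions.

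| N | Ratio-scale interaction significant | Rate-difference interaction significant | Active-arm predictor significant |
|---|---|---|---|
| 300 | 2.3% | 16% | 75% |
| 600 | 4.7% | 27% | 98.5% |
| 1000 | 3.7% | 41% | 100% |

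The ratio-scale test stays at or below its false-positive rate. The rate-difference test is not blind, but it is weak. The contrast it had to detect was 0.35 × (0.11 − 0.0223) = 3.07 per 100 woman-years. That lies between the contrasts in step 2 (5.13 − 2.57 = 2.56 and 5.78 − 1.93 = 3.85). Power at the step 2 rates was not simulated.

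**4. Chance findings.** No alpha or multiplicity rule is given for the interaction tests. At 0.05 with independent tests and no true interaction, the chance of at least one flag is 1 − 0.95^m: 40%, 64% and 87% for m = 10, 20 and 40. The number of characteristics is not stated.

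**5. Techniques 2 and 3.** If technique 2 stratifies only on characteristics flagged by technique 1, it inherits the same limit. Technique 3 readily finds predictors, but of fracture on the drug. With a constant relative effect, those are the high-risk women with the larger absolute benefit, so taking low predicted fracture to mean benefit would point the wrong way.

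**The case against.** The strongest reply is that the ratio scale suits the protocol's own puzzle. Its background asks why treatment might fail in frail women, and the previous ZEST study saw no fracture reduction trend. That is a question about a varying relative effect, which a ratio-scale interaction addresses. A constant 0.65, from a trial in healthier women, is a case the protocol doubts. This stands as a reason to keep the interactions. It does not make them sufficient, because the stated aim is to find who gains most and a constant ratio is not ruled out.

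A second reply is that the technique 1 model already contains each arm's rate at each level, so differences need only exponentiation. That is true, and it makes the fix cheap, but the plan does not commit to reporting them.

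A reader might infer more than the text supports:

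- **That Aim 3(a) works on ratio scales alone.** Technique 3 has no interaction term, and the laboratory models can give differences in raw change. Neither measures fracture benefit.
- **That technique 2 is certainly gated by technique 1.** This is the natural reading of its back-reference, but not an explicit rule, and absolute estimates are not excluded.
- **That absolute benefit differs nearly four-fold.** A 3.75-fold gap is only the ratio of two assumed rates, 0.30/0.08. Setting 0.11 against 0.0223 gives 3.97 in 3-year risk, but this compares nonvertebral incidence with a major-fracture threshold, and a population average with one of three entry routes.

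**Conclusion.** The point holds for the between-arm fracture tests in Aim 3(a). As written they can reveal only a varying rate ratio, and no absolute measure accompanies them. Under a constant relative effect the plan would find no true target group, although it might well report a chance one.

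On the protocol's own 2-3x gradient, what would go unreported is a 2- to 3-fold difference in fracture rate reduction, or about 1.5- to 2.7-fold in 3-year risk. The rate figure requires only a constant ratio. The risk figure also rests on RR 0.65, a constant hazard, three full years of follow-up, and lower-group rates of 0.0223 to 0.11; the protocol expects some women to die or leave earlier. Larger gaps are illustrative only. The same logic applies to adverse events on the odds scale, but the documents give no event rates from which to size it.

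The aim is exploratory, and its wording (potentially differential effects, preliminary estimates) is suitably cautious. Nothing here touches the primary test. This is a worthwhile improvement to how the trial answers its own question.

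**What to change.** Keep the one-at-a-time interactions and add one prespecified table to the SAP, using both arms:

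- **Rows: baseline risk.** For example, baseline FRAX major-fracture probability, and prior spine or hip fracture yes/no. FRAX already serves one entry route (women who "would be treated based on FRAX" thresholds), so it should be computed for all women whose inputs are available. The documents do not show how well FRAX separates risk in these residents, and they name falls and mobility as important, so it should not be the only risk measure.
- **Fracture columns.** Each arm's predicted fracture rate from the negative binomial model, the rate ratio, and the rate difference per 100 woman-years, with 95% CIs for both effect measures.
- **Harm columns.** Risk differences with 95% CI for key harms, such as those the protocol singles out: falls, atrial fibrillation, stroke and symptomatic hypocalcemia.

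State that the judgement of who benefits most rests on these estimates and intervals, not on a significance rule. Any trend test in the rate difference is supportive only, given its low power. Say also which characteristics technique 2 will stratify on and on which effect scale, and that technique 3 predicts fracture on treatment, not benefit.

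The cost is a SAP paragraph, some model-based prediction, and FRAX calculation for women who entered on T-score or prior fracture. Intervals will be wide, and the report should say so.

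### Aim 3(a) flags effect modifiers from an open-ended series of one-at-a-time interaction tests and then estimates subgroup effects for them in the same data, with no stated multiplicity handling or correction for selection.

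*Protocol*

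**What the plan says.** The procedure is in the Protocol, Statistical Considerations, in the paragraph on Aim 3(a). It has three linked parts.

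- **Screen.** The plan says "we will include all baseline clinical and laboratory characteristics, one-at-a-time, as an additional fixed effect in the models above", each with a treatment interaction. Under Main Analyses, those models are negative binomial regressions "with each fracture outcome as the dependent variable", linear models for the laboratory safety measures (raw and percent change), and logistic models for adverse events ("any and specific types of adverse events").
- **Rule.** "Statistical significance of the interaction term will be interpreted as a patient baseline characteristic whose levels exhibit potentially differential treatment effects". The same sentence extends the rule to safety.
- **Estimation.** "Second, we will stratify analyses by such baseline criteria to actually obtain preliminary estimates of subgroup-specific treatment effects/safety differences".

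The Protocol does not list or count the characteristics. The only significance level it gives is for the main hypothesis: "significance at $\alpha=0.05$ level for the primary outcome of all new fractures will serve as a formal test". Backward elimination and tree pruning are named as guards against overfitting, but only for the later prediction models in the active arm. The SAP does not mention subgroups or interactions.

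**The concern.** Aim 3(a) sets out to identify the residents most likely to benefit from zoledronic acid or least likely to be harmed by it. Two problems follow from the procedure as written.

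First, many tests are made under a rule that reads each significant one as a possible modifier. Some will be significant by chance, and a reader who is not told how many were run cannot discount for that.

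Second, an estimate looked at because it passed a significance threshold is on average too far from no interaction when it comes from the data that selected it. This holds for any number of tests, and it applies to true modifiers as well as false ones.

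What is at stake is the credibility of any sub-population the trial puts forward.

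**Working it through.** The documents give no false-positive rate for this screen, so there is no stated figure to reproduce.

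**Inputs**

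- Number of characteristics, k: not stated. The Protocol names roughly 20-24 candidates: 11-12 laboratory and skeletal measures, five concomitant treatments or devices, and items such as age, prior fracture, FRAX, setting, assistive device and prior bisphosphonate use. That all are recorded and tested is an assumption.
- Level per interaction test: not stated. I assume 0.05 two-sided and show 0.01 and 0.10.
- Fracture outcomes: three (all, nonvertebral, vertebral), from Study Objectives.
- Total fractures, D: not stated. I assume 100-200.

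**Step 1. Chance of at least one false flag, one outcome, no true interaction, independent tests**

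Formula: 1 − (1 − α)^k.

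- k = 10: 1 − 0.95^10 = 40%
- k = 20: 1 − 0.95^20 = 64%
- k = 30: 1 − 0.95^30 = 79%

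The chance passes 50% at k = 14 for α = 0.05, at k = 7 for α = 0.10, and at about k = 69 for α = 0.01. At k = 20 it is 18% for α = 0.01 and 88% for α = 0.10.

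**Step 2. Correlated tests**

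Baseline bone and laboratory measures are probably correlated. I simulated exchangeable correlation r among the test statistics (200,000 draws, α = 0.05).

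| k | r = 0 | r = 0.3 | r = 0.5 |
|---|---|---|---|
| 20, one outcome | 64% | 54% | 42% |
| 24, one outcome | 71% | 59% | 46% |
| 12, three fracture outcomes | 78% | 71% | 61% |
| 20, three fracture outcomes | 92% | 85% | 74% |

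The three-outcome rows assume correlation 0.6 between outcomes. Correlation does not change the expected number of false flags. At k = 20 it is 20 × 0.05 = 1 per outcome, or 3 over three fracture outcomes. Laboratory and adverse-event models would add to this.

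**Step 3. Smallest interaction that can be flagged (fracture models, Poisson approximation, equal arms)**

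- Binary characteristic, events split evenly over four cells: SE of the log ratio of IRRs = sqrt(4 × 4/D) = sqrt(16/D), which is 0.40 at D = 100 and 0.28 at D = 200. The smallest significant ratio is exp(1.96 × SE) = 2.2 and 1.7.
- Continuous characteristic, per SD: each arm's slope has variance of about 1/(D/2), so the difference has SE = sqrt(4/D) = 2/sqrt(D), which is 0.20 and 0.14. The smallest significant ratio is about 1.5 and 1.3 per SD.

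An uneven split or overdispersion makes these thresholds larger.

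**Step 4. Exaggeration after selection at |z| > 1.96 (simulated)**

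- True interaction zero: mean absolute estimate 2.3 SE.
- True interaction 1 SE: 2.5 SE, overstated about 2.5-fold.
- True interaction 2 SE: 2.8 SE, overstated about 1.4-fold.

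This step needs no assumption about k.

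**The case against.** The strongest reply is that the plan hedges this work properly. It describes a partly exploratory, data-mining exercise, calls the differences potential and calls the estimates preliminary. Nothing makes a flagged subgroup confirmatory. Wide unadjusted screening is a common way to generate hypotheses, and strict error control could suppress true modifiers, which is costly where the screen covers safety. Much of this stands. It is a reason not to impose a multiplicity gate. It does not remove the selection bias in the estimates, and it does not tell readers how many tests lie behind a flag.

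Several stronger readings are tempting, but the documents do not support them:

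- *A false subgroup is more likely than not.* This needs k and α, and neither is given. For one outcome it takes at least 14 independent tests at 0.05, and at k = 20 with correlation 0.5 the chance is 42%.
- *Testing is at an unadjusted 0.05.* That is an inference from silence, since the level is stated only for the main hypothesis.
- *Any flagged interaction must show at least a 1.7- to 2.2-fold difference.* That holds only for a binary characteristic under the assumed fracture counts. Many candidates are continuous, and the figure does not apply to the laboratory or adverse-event models.
- *Only significant characteristics are ever stratified.* The text points that way for Aim 3(a) but does not say so exclusively. Main Analyses also stratifies by institutional setting regardless of significance.
- *The main fracture conclusion is compromised.* It is not, because that hypothesis has its own separate test.

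**Conclusion.** The concern holds in a limited form. Following Aim 3(a) as written gives subgroup estimates that are selected by significance and reported from the same data, with no stated correction. Those estimates will be biased away from no interaction: about 2.5-fold for a true interaction of one standard error, and about 1.4-fold for one of two.

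Some flags are also likely to be false, but how likely is conditional. At 0.05 with no true interaction, it is 40-79% for one outcome over 10-30 independent tests, lower with correlation, and about 74-92% over three correlated fracture outcomes with 20 characteristics. The number of characteristics, the interaction level, the correlations and the fracture count are assumptions, because the documents do not give them.

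The consequence is confined to Aim 3(a). It should be corrected, but it does not threaten the trial's main result.

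**What to change.** Replace stratification by significant criteria with the following:

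1. Report the number of interaction tests made for each outcome.
2. For every characteristic, whatever its significance, give the interaction estimate with its confidence interval from the interaction model: a ratio of IRRs for fractures, a ratio of odds ratios for adverse events, a difference for laboratory measures.
3. For each flagged characteristic, show a shrunken or bootstrap bias-corrected estimate beside the raw one, and label it hypothesis-generating. The bootstrap should repeat the selection step.
4. If wanted, show false-discovery-adjusted p-values alongside as an aid to reading. They should not decide what is reported, particularly for safety.

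The cost is SAP wording, a little more analysis and a longer table. Subgroup estimates will look less striking. No new data are needed and no exploration is ruled out.
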